**8. Procedures Involved - Describe procedures including:**

**Procedures**

*This study will consist of two collections separated by at least 48 hours. Each testing session will take approximately 2.5 hours to complete. All testing procedures will be administered pre and post a session of transcranial direct current stimulation (tDCS). The primary investigator ([name]) will collect all data. Doctoral students will assist data collection. The PI retains the right to stop testing if he determines that any aspect of the protocol puts the participant at more than minimal risk.*

*Individuals <18 years old will only complete strength testing and questionnaires at one testing session.*

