**Data Analysis**

Independent t-tests will be used to examine demographic differences between the two groups. A 2 (limb) x 2 (group) ANOVA will be used to evaluate differences in strength, TMS, and fNIRS measures. Regression analyses will be used to determine the relationship between the CNS measures and quadriceps strength, and the relationship between the TMS and fNIRS measures.

**9. Compensation or Credit - Describe the amount and timing of any compensation or credit to participants. Identify the source of the funds to compensate participants**

*Each participant (≥18 years of age) will be paid \$100 for their participation in this study. Participants must complete both sessions to receive the compensation.*

*Each participant (<18 years of age) will receive \$50 for their participation in this study as they will only complete one session.*

**10. Risk to Participants - List the reasonably foreseeable risks, discomforts, or inconveniences related to participation in the research. Consider physical, psychological, social, legal, and economic risks.**

*Risks associated with Testing Procedures (TMS, strength testing)*

*There are no known long term risks of TMS. There is a very small risk of seizure, syncope, and change in auditory thresholds. A recent study examining adverse events of TMS concluded: "Our data suggest that single/paired-pulse and repetitive TMS, conducted within the published guidelines pose a very small increment over the background risks of everyday life to subjects without known risk factors." Screening potential participants for a prior history of seizures, syncope, and hearing impairments will allow us to exclude individuals at increased risk. Participants will be offered ear plugs if the sound from the TMS pulse is uncomfortable.*

*In the very unlikely event of a seizure, the following steps will be taken: 1) The participant will be positioned in the safest position to maintain an open airway (i.e. laying supine or side lying), 2) emergency personal will be contacted by dialing 911 (research assistant), 3) any objects will be moved away from the participant to prevent additional injury, 4) monitor vitals until emergency personal arrive.*

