*Most subjects report no discomfort from TMS although some do report mild discomfort over the site of stimulation. Some subjects report a mild headache following the procedure. This typically resolves within 24 hours and can be treated with over the counter analgesics (i.e. Tylenol, ibuprofen). If subjects do experience discomfort over the stimulation site, the intensity of the stimulator can be reduced to minimize this. The session will be terminated immediately if the subject reports discomfort that is beyond their tolerance. Subjects may experience mild muscle soreness 24-48 hours after the testing session. This is a normal physiologic response to strength testing and strength training. There are no risks or discomfort associated with strength testing. Strength testing is performed at regular intervals after ACL reconstruction.*

*Risks associated with transcranial direct current stimulation (tDCS)*

*tDCS have been used in a growing number of laboratories worldwide since 1985. In the present protocol, only a non-significant risk protocol is being employed by using tDCS. tDCS is very safe and there have been very few incidences of adverse events with tDCS. A recent meta-analysis of adverse effects associated with tDCS reviewed 209 experiments (3836 subjects). The main adverse events were itching, tingling, headache, discomfort, and burning sensation. Poreisz et al summarized findings from 567 sessions involving 102 participants to demonstrate that adverse effects were quite minor in severity. For example, mean ratings of itching during stimulation were 1.6 out of 5. Similar ratings were given for tingling (1.74), burning (1.59), headache (1.4), pain (1.41), difficulties in concentrating (1.73), nervousness (1.0), and unpleasant sensation (1.24). The highest rated adverse effect was fatigue (2.17), although the authors note that this factor was likely influenced by the completion of sometimes monotonous tasks while also receiving tDCS.*

*There is a strong evidence that tDCS is extremely safe. A recent review reported that "To date, based on over a total 33,000 sessions and over 1000 subjects who received repeated tDCS sessions, there is no evidence for*

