*irreversible injury produced by conventional tDCS protocols within a wide range of stimulation parameters ( $\leq 40$  min,  $\leq 4$  mA,  $\leq 7.2$  C). In our protocol, the dose of tDCS is significantly below the dose ( $\leq 2$  mA, 20 min) described here. An even more recent systematic review (2018) concluded that “Little evidence was found to suggest that repeated sessions of active tDCS poses increased risk to participants compared to sham tDCS within the limits of parameters used to date.” However, in case of an unlikely adverse event, we will have appropriate measures to ensure participant safety and comfort. If there is any discomfort during the tDCS procedure, we will double-check our electrodes and machine settings. In case of a headache/neck pain after tDCS, the participant will be advised to take an over-the-counter pain medication. In an unlikely event of skin burn, participant will be referred/ directed to a physician for medical management. Patient and/or his/her medical insurance will pay for the care. This will be made clear in the informed consent.*

*We will assess any discomfort or adverse event before, during or after tDCS in patients and age-matched controls. We do not anticipate any major adverse events. Only minor discomfort in less than 5% of subjects undergoing tDCS experience is transient headaches or soreness at the site of stimulation. These side-effects are believed to be due to stimulation of muscles and nerves near the stimulating coil. During and following every tDCS session, we will ask the participant about any incidence of headache. If the participant complains of any discomfort or pain during the tDCS session, the session will be terminated at once. Participants will be informed that if they should feel a tingling sensation below the electrodes. If they feel any other uncomfortable sensation such as burning, they should inform the investigators. If the participant informs us of uncomfortable sensation, we will ensure electrode/machine settings are correct. If the uncomfortable sensation continues, we will stop the procedure.*

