*In order to ensure participant safety following the session, we will use the questionnaire proposed by Brunoni et al. 2011 after each session to record any adverse effects, and follow-up with participants the day after each session if they report scores of 3 (moderate) or 4 (severe) for any of the symptoms or side effects. Anyone self-reporting a severe effect (4) will be withdrawn from the study.*

Risks associated with stationary bike riding

*There is very minimal risk involved with stationary bike riding in our population of athletic individuals. Additionally, stationary bike riding is part of standard physical therapy early (prior to 4 months which is the earliest time that we would recruit a participant) after ACLR. During the intervention (stationary bike with tDCS), participant tolerance will be assessed subjectively (rating of perceived exertion, symptoms) at regular intervals, and the exercise will be terminated if signs or symptoms indicate poor tolerance. In addition, the protocol will include warm-up and cool down phases to minimize the risk of musculoskeletal injury. If required, the participants will be provided with water before, during or after the exercise.*

**11. Potential Benefits to Participants - Realistically describe the potential benefits that individual participants may experience from taking part in the research. Indicate if there is no direct benefit. Do not include benefits to society or others.**

*Results of the strength test will be provided to participants in both groups. The results of the strength test will benefit participants in the ACLR group as the findings indicate whether additional strengthening is required and if progression into the next stage of rehabilitation is warranted. The results do not provide any benefits to participants in the uninjured group.*

**12. Confidentiality - Describe the following measures to ensure the confidentiality of data: Who will have access to the data? Where and how data will be stored? How long the data will be stored? How and when will data be de-identified?**

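### An adult who rates a symptom severe after session 1 is withdrawn and, as section 9 is written, forfeits the whole $100

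*Protocol*

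**What the plan says.** **Payment (Protocol, section 9, Compensation or Credit).** Each adult "will be paid \$100 for their participation in this study", on one condition: "Participants must complete both sessions to receive the compensation". No part payment is described, and there is no exception for a safety stop or withdrawal. Minors receive $50 "for their participation in this study as they will only complete one session".

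**Sessions (Protocol, section 8, Procedures).** "This study will consist of two collections separated by at least 48 hours".

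**Severe effects (Protocol, section 10, Risk to Participants).** An adverse-effect questionnaire is completed after each session. A score of 3 (moderate) or 4 (severe) leads to contact the next day. In addition, "Anyone self-reporting a severe effect (4) will be withdrawn from the study".

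**Discomfort during a session (Protocol, section 10).** For tDCS one sentence reads "If the participant complains of any discomfort or pain during the tDCS session, the session will be terminated at once". The same part of the section says that electrode and machine settings are checked first, and then "If the uncomfortable sensation continues, we will stop the procedure". For the testing procedures the threshold is different again: "The session will be terminated immediately if the subject reports discomfort that is beyond their tolerance".

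**The concern.** Severity grading, next-day contact and withdrawal all depend on what the participant chooses to say. Section 9 attaches the whole adult payment to completing both visits, and section 10 ends participation on a self-rated 4. Neither section refers to the other, so the effect looks unintended, but an adult deciding how to score a symptom after session 1 has $100 resting on the answer.

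Two things are at stake. The first is participant protection: someone who feels unwell has a reason to score lower and come back. Section 10 also places the cost of care for a skin burn on the patient or the patient's insurer, so an affected adult could lose the payment and bear that cost as well. The second is the quality of the adverse-effect record. Section 1 presents this study as the pilot for a larger application involving multiple tDCS sessions, so an accurate count of severe effects has some value beyond this trial.

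**Working it through.** There is no statistical figure to reproduce. The check is to read the payment, withdrawal and stopping rules together and follow each case to its payment.

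**Inputs**
- Adult payment: $100 in total, conditional on both sessions (section 9).
- Payment to a minor: $50 for one session (section 9).
- Adult sessions: 2, at least 48 hours apart (section 8).
- Score of 4: withdrawal. Score of 3 or 4: next-day contact (section 10).

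**Payment under the rules as written**

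| Case | Payment |
|---|---|
| Adult scores 4 after session 1 and is withdrawn | $0 |
| Adult scores 3 after session 1, is contacted, completes session 2 | $100 |
| Adult scores 4 after session 2 | $100 (both sessions already done) |
| Adult's session is stopped for discomfort | $0 or $100, not determined by the text |
| Minor completes the single session | $50 |

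**Size of the penalty**
- A 4 rather than a 3 after session 1, for an adult who would otherwise finish: $100 − $0 = $100, which is 100% of the payment.
- The same severe report after session 2: $100 − $100 = $0.
- Against the protocol's own one-session payment: $50 − $0 = $50 less than a minor receives, although under sections 5 and 8 minors have neither TMS nor tDCS.

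The first result needs no interpretation. The payment condition and the withdrawal rule are each stated without exception, and a participant withdrawn after session 1 cannot complete session 2.

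**The discomfort route**
This route does not close in the same way. The tDCS text says both that any complaint ends the session at once and that the procedure stops only if the sensation persists after a settings check. Whichever applies, section 9 does not say whether a session stopped by staff counts as completed, and section 10 does not say that the participant may not return. Forfeiture therefore depends on two points the text leaves open.

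**What under-scoring would lose**
An adult who shades a 4 down to a 3 still triggers the next-day contact. What is lost is the withdrawal and the record of a severe effect. The payment rule gives no further reason to go below 3.

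**The case against.** The strongest case against this point is that it is narrow and may rarely arise. It bites only for a score of 4, only after session 1 and only for adults. Section 10 cites mean symptom ratings between 1.0 and 2.17 out of 5 from earlier sessions and expects minor discomfort in fewer than 5% of subjects, so severe scores should be few. The aims in section 1 concern corticospinal excitability and quadriceps performance; tolerability is not an aim, a hypothesis or an analysis listed under Data Analysis. All of this stands, and it limits the weight of the point without removing it.

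The consent forms, which section 13 says are attached, were not available here and might describe payment after early stopping. That is possible, but part payment there would contradict section 9 as written, so the two would still need to be aligned.

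The comparison with minors is also loose. Their $50 pays for everything asked of them, at a lighter visit. It shows that the protocol has a one-session amount, not that adults were meant to be paid by session.

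A reader might infer three stronger things that the documents do not support:
- *That any complaint of discomfort costs an adult the payment.* The stopping rules conflict, and a completed session is not defined.
- *That the next-day safety contact is defeated.* A score of 3 still triggers it.
- *That adverse-effect data are biased more under active than under sham stimulation.* No figure in the protocol bears on this.

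**Conclusion.** The point holds in a limited form. As written, an adult who self-reports a severe effect after session 1 loses the full $100, while one who reports a moderate effect can continue and be paid. That is a financial reason to under-report severe effects and to carry on while unwell, and it is absent after session 2. The conclusion rests only on reading sections 9 and 10 as they stand, and on there being no exception in the consent form.

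Loss of payment after a session stopped for discomfort is possible but not established. The amount of under-reporting, and any difference between active and sham, cannot be computed from the document. Nothing here affects the trial's stated aims. It is an inexpensive improvement to participant protection and to the adverse-effect record, and worth making for that reason.

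**What to change.** Replace the adult payment condition in section 9 with wording such as: *Adults are paid $50 for each session started. A session stopped because of a reported symptom is paid in full. Withdrawal because of a reported symptom does not forfeit payment for any session already started.* Put the same statement in the adult consent form.

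Separately, reconcile the two tDCS discomfort rules in section 10. This is for the investigator to settle. The payment change does not depend on how it is settled and implies no change to any stopping or withdrawal rule.

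**Cost per case (payment after the change minus payment now)**
- Withdrawal during or after session 1: $50 − $0 = $50. An adult who attends session 1 and does not return for an unrelated reason would also receive this $50.
- Session 2 stopped for a symptom: $100 − $0 = $100 if such a session would now go unpaid, or $100 − $100 = $0 if it already counts as completed. The same range applies if session 1 is stopped and the adult returns and completes session 2.

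**Scale**
Section 6 plans 30 + 30 = 60 participants. If all were adults, the most payable is 60 × $100 = $6,000, and the change does not raise that ceiling. It is an upper bound, since minors may enrol. The number of early stops is not given, so as an assumption:

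| Early stops | At $50 each | At $100 each |
|---|---|---|
| 1 | $50 (0.8% of $6,000) | $100 (1.7%) |
| 3 | $150 (2.5%) | $300 (5.0%) |
| 6 | $300 (5.0%) | $600 (10.0%) |

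The other costs are a minor amendment and a slightly weaker incentive to return for session 2.

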**14. HIPAA:**

**a) Is any of the data coming from covered entities\* under HIPAA?**

Yes       No

**IF YES, please describe:**

**b) Is a data use agreement\*\* required?**

Yes       No

**c) Is a HIPAA Waiver of authorization\*\*\* requested?**

Yes       No

**\* Covered Entity**- A health plan, a health care clearinghouse, or a health care provider who transmits health information in electronic form in connection with a transaction for which HHS has adopted a standard.

**\*\* Data Use Agreement**- An agreement into which the covered entity enters with the intended recipient of a limited data set that establishes the ways in which the information in the limited data set may be used and how it will be protected.

**\*\*\* Waiver of Authorization**- The documentation that the covered entity obtains from a researcher or an IRB or a Privacy Board has waived or altered the Privacy Rule's requirement that an individual must authorize a covered entity to use or disclose the individual's PHI for research purposes.

**15. Conflicts of Interest**

**a) Do you or any member of your research group, spouses or any dependent children have any interest (i.e. any property of financial interest including stock in the sponsor company, patents, trademarks, copyrights or licensing, supplemental research grants or consulting arrangements) in the test drug/product, device, or research procedure that is the subject of this study that could affect any of the following: the study outcome, data analysis, enrollment of subjects, study design.**

Yes       No

**IF NO,** please move on to section 16.

**IF YES,** please disclose below and the ways in which the researchers will minimize harm to research subjects and/or the objectivity of research. Please discuss how these conflicts will be managed during the period of the trial. Include language disclosing such interest in the consent form for the use by research subjects.

In addition, for industry-sponsored trials, please attach the documentation submitted to the sponsor as required by [21CFR54.1](#), if applicable.

**b) If related to a grant, have all investigators filed a current annual Significant Financial Interest Form?**

Yes       No

**c) Among the research team, is there any financial interest that could affect any of the following: the study outcome, data analysis, enrollment of subjects, study design?**

Yes       No

**IF YES,** please describe and disclose in the consent form.

**d) Are there any plans for commercial development related to the findings of this study?**

Yes       No

**IF YES,** please describe

